## 9.2 POPULATIONS FOR ANALYSES

All enrolled subjects will be included for analyses.

#### 9.3 STATISTICAL ANALYSES

## 9.3.1 GENERAL APPROACH

Baseline patient and operative characteristics will be compared between the two groups using Kruskal-Wallis test for continuous variables and chi-square test for categorical variables. A multivariate logistic regression will be conducted to determine independent associations between stone-free rate and certain candidate predictors chosen a priori, including patient position, number of stones, and stone volume.

# 9.3.2 ANALYSIS OF THE PRIMARY ENDPOINT(S)

Stone free rates for each laser will be analyzed using the Kruskal-Wallis statistical test. Multiple multivariate regression will also be used to control for stone size, operative time, and other potential confounders.

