# 1.1 SYNOPSIS

Title:	SUPERPULSED THULIUM FIBER LASER VS. PULSE MODULATED HIGH POWER HOLMIUM: YAG LASER FOR RETROGRADE INTRARENAL SURGERY
Grant Number:	N/A
Study Description:	
 
This is a randomized prospective study comparing the stone free rate and operative efficiency of two leading contemporary laser systems used during retrograde intrarenal surgery for kidney stone disease. We will compare the following two systems:
 
1. A superpulsed thulium fiber laser (thulium)
 
2. A pulse modulated high power holmium laser (Holmium)
 

Objectives * :	Aim: To determine which laser system has superior outcomes as measured by post-operative stone-free status and intraoperative efficiency metrics
	Research Question: During retrograde intrarenal surgery for kidney stone disease, which contemporary laser system (thulium vs. holmium) has a superior stone free rate?
	Null hypothesis: During retrograde intrarenal surgery for kidney stone disease, there is no difference in stone free rates between the two laser systems.
	Alternative Hypothesis: During retrograde intrarenal surgery for kidney stone disease, the thulium laser has a superior stone free rate.
Endpoints * :	
 
Primary Endpoint:
 
Stone-free status as determined by a post-operative CT scan.
 

	
 
Secondary Endpoints:
 
The secondary endpoints to be collected will pertain to efficiency metrics as produced by the laser systems: 
 
Fragmentation speed = stone volume/lasing time (mm3/sec)
 
Energy Utilization = Laser energy/volume of stone (J/mm3)
 
Lasing Activity: Lasing time/lithotripsy operative time (%)
 
Operative time (minutes)
 
Lasing time (seconds)
 
Lithotripsy operating time (seconds)
 
Treatment time (seconds)
 
 
 

Study Population:	We anticipate a sample size of 82 subjects enrolled in this study. Adult patients 18-years of age and older with non-obstructing kidney stones undergoing planned retrograde intrarenal surgery with laser lithotripsy.
Description of Sites/Facilities Enrolling Participants:	[name] currently operates twice a week at Mount Sinai West (formerly Mount Sinai Roosevelt Hospital), located at [name]. In addition, he sees patients in the clinic at the following sites: Department of Urology Faculty Practice at [name]; Midtown Urology FPA at [name].

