# **3** OBJECTIVES AND ENDPOINTS

OBJECTIVES	ENDPOINTS	JUSTIFICATION FOR	PUTATIVE
		ENDPOINTS	MECHANISMS OF
			ACTION
Primary			
To determine which laser	Stone free status as	Stone free status on 2 month	N/A
system (if any) offers superior	determined by 2-	follow up CT scan is the most	
efficacy.	month postoperative	accurate evaluation for complete	
	CT scan	resolution of a patient's kidney	
		stone burden	

OBJECTIVES	ENDPOINTS	JUSTIFICATION FOR	PUTATIVE
		ENDPOINTS	MECHANISMS OF
			ACTION
Secondary			
To determine which laser system (if any) offers superior efficiency.	Fragmentation speed, lasing activity, and energy utilization	These intraoperative laser metrics allow for the evaluation of intraoperative laser efficiency	N/A

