## 6 STUDY INTERVENTION(S) OR EXPERIMENTAL MANIPULATION(S)

## 6.1 STUDY INTERVENTION(S) OR EXPERIMENTAL MANIPULATION(S) ADMINISTRATION

#### 6.1.1 STUDY INTERVENTION OR EXPERIMENTAL MANIPULATION DESCRIPTION

For subjects receiving URS, randomization will occur preoperatively. These subjects will be randomized to undergo lithotripsy with either Ho:YAG or TFL lasers.

All subjects will undergo surgical interventions that abide by broadly accepted guidelines and standards of care, allowing for slight variations in technique as seen necessary by the attending surgeon [name].

The type of laser that is chosen in SOC is based on hospital availability. That is, most hospitals only have one laser type to choose from (and that laser type is generally contingent on the biomedical contracts the

hospital holds with the various laser manufacturers). We are uniquely situated at Mount Sinai West in that we have multiple laser systems to choose from. Multiple surgeons share the lasers, and typically [name] will use whichever laser is already in the room or readily available. Approximately 50% of ureteroscopies were performed with each laser, +/- 10%.

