## 6.3 MEASURES TO MINIMIZE BIAS: RANDOMIZATION AND BLINDING

Patients will be randomized to receive either Thulium or Holmium laser lithotripsy. Patients will be blinded as they will be anesthetized during the operation. Blinding of the operators would not be possible owing to the differences in laser modalities.

We will utilize random.org which is a validated tool that utilizes atmospheric noise to generate random numbers. Each enrolled patient will be given a subject ID and these study IDs will be entered as string of integers to random.org and randomized prior to the initiation of the study. This process will determine group assignments. This will ensure both true randomization and equal allocation.

7 STUDY INTERVENTION/EXPERIMENTAL MANIPULATION DISCONTINUATION AND PARTICIPANT DISCONTINUATION/WITHDRAWAL

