# 9.3.3 ANALYSIS OF THE SECONDARY ENDPOINT(S)

Fragmentation speed, energy utilization, lasing activity, operative time, lasing time, lithotripsy time, and treatment time will be analyzed using Kruskal-Wallis statistical tests and multivariate regression to predict differences in levels of renal-damage associated biomarkers.

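### The primary-endpoint regression adjusts for operative time, which arises after randomisation and is itself a secondary endpoint, so the adjusted laser effect can be distorted

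*Combined protocol and SAP*

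**What the plan says.** Section 9.3.2 gives two analyses of the primary endpoint. The first is unadjusted: "Stone free rates for each laser will be analyzed using the Kruskal-Wallis statistical test". The second is a regression: "Multiple multivariate regression will also be used to control for stone size, operative time, and other potential confounders".

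Other sections settle what kind of variable operative time is:

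- **Timing.** Section 6.1.1 states: "For subjects receiving URS, randomization will occur preoperatively". Operative time therefore comes into being after allocation.
- **Role in the synopsis.** It is one of the secondary endpoints, which are introduced as "efficiency metrics as produced by the laser systems".
- **Role in Section 9.3.3.** It is an outcome: "operative time, lasing time, lithotripsy time, and treatment time will be analyzed".

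Section 9.3.1 separately describes a logistic regression for stone-free status with patient position, number of stones and stone volume as predictors chosen in advance. Operative time is not among those named. No section describes a mediation analysis or a direct-effect estimand.

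**The concern.** A confounder of a treatment comparison must influence which treatment is given. Operative time cannot do so here, because the laser is assigned before the operation starts. The plan treats the same variable as a possible effect of the laser in 9.3.3 and as a nuisance to be removed from the laser effect in 9.3.2.

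If the lasers differ in operative time, conditioning on it does two things:

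1. It removes, wholly or in part, any laser effect on stone clearance that acts through time.
2. It links arm to unmeasured case difficulty. Suppose thulium is faster. A thulium case and a holmium case with the same operative time are then not alike: the thulium case was probably the harder one, and harder cases leave more residual stone. The adjusted comparison is then biased against thulium. If thulium is slower, the bias runs the other way.

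What is at stake is the adjusted laser effect on the primary endpoint. It could disagree with the unadjusted result because of the covariate and not because of the lasers.

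**Working it through.** **The plan's own figure.** Section 9.1 gives 33 per arm for 66% versus 33%, 80% power and 5% alpha. Two-sided, with unpooled variance:

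n = [p1(1−p1) + p2(1−p2)] × (1.96 + 0.84)² / (p1−p2)² = (0.2244 + 0.2211) × 7.84 / 0.1089 = 32.1, so 33 per arm.

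With 20% dropout, 66 / 0.80 = 82.5, against 82 stated. The figure reproduces. It rests on an unadjusted comparison of two proportions, and nothing below changes it.

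**What the documents do not give.** They contain no laser effect on operative time, no relation between operative time and stone-free status, and no measure of case difficulty. The inputs below are assumptions.

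**Check 1: large-sample bias (N = 400,000).** Let A = 1 for thulium, S = stone size, U = unmeasured difficulty, T = operative time and e = noise; S, U and e are standard normal.

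- T = aA + 0.5S + uT·U + e
- logit P(stone free) = −0.3 + bA + gT − 0.5S + uY·U

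Thulium shortens T by 0, 0.5 or 1 unit (a = 0, −0.5, −1). Entries are risk differences in percentage points, in that order.

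| Scenario | True difference | Adjusted for stone size and T |
|---|---|---|
| Effect only through time (b = 0, g = −0.6, uT = uY = 0) | 0 / 6 / 12 | about 0 in all three |
| No effect, difficulty drives both (b = 0, g = 0, uT = 1, uY = −1) | 0 / 0 / 0 | 0 / −5 / −10 (OR 1.00 / 0.79 / 0.64) |
| Direct effect, difficulty drives both (b = 0.8, g = 0, uT = 1, uY = −1) | about 16 in all three | 16 / 11 / 6 |

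Adjusting for stone size alone recovers the true difference in every row.

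**Check 2: behaviour at the planned size (33 per arm).** V is standardised stone volume, D is unmeasured difficulty and δ is the reduction in operative time under thulium, in within-arm SDs.

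- T = −δA + 0.5V + 0.5D + √(1 − 0.25 − 0.25)·e, so V and D each correlate 0.5 with T within arm
- logit P(stone free) = c − 0.7V − 0.7D, with c set in each arm to give 50% in both arms (type I error) or 66% versus 33% (power)
- Time itself has no effect on stone-free status

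There were 6,000 replicates per scenario, with Monte Carlo standard error about 0.3 to 0.4 points for type I error and 0.5 to 0.8 points for power.

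| | δ = 0 | 0.25 | 0.5 | 1 |
|---|---|---|---|---|
| No true effect: median time-adjusted OR | 0.99 | 0.91 | 0.78 | 0.64 |
| No true effect: type I error, time-adjusted | 4.9% | 5.6% | 6.5% | 9.7% |
| 66% vs 33%: power, time-adjusted | 80% | 75% | 67% | 42% |
| 66% vs 33%: unadjusted and time-adjusted tests on opposite sides of p = 0.05 | 8% | 10% | 16% | 37% |

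For comparison, type I error is 4.6–5.1% with volume-only adjustment and 5.1–5.6% unadjusted. Power is 80–82% and 78–80% respectively. Those two tests disagree in about 7% of trials, so that much disagreement is ordinary noise. A repeat with 10,000 replicates agreed: at 1 SD, type I error 10.0%, power 43%, disagreement 36%.

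**Sensitivity.**

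- Thulium lengthens time by 0.5 SD: the distortion reverses, with median OR 1.27 under no true effect.
- Weaker link (difficulty–time correlation 0.3): type I error about 6% at 0.5 SD and about 7% at 1 SD; power 71% and 54%.
- No link to difficulty: no bias, but power still falls from 82% to 68% at 1 SD, because time is collinear with arm.

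**The case against.** The strongest defence is that the regression is only supporting. Section 9.3.2 puts the Kruskal-Wallis test first and adds the regression afterwards, and Section 9.1 sizes the trial on two unadjusted proportions. The natural reading is that the unadjusted test leads, and operative time does not touch it. This limits the harm. But the regression stands under the primary-endpoint heading, no text ranks the two results, and an adjusted estimate is easily read as the more definitive one.

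A second point is that the lasers may not differ in operative time, in which case no bias arises. That is true, but efficiency is an open question of the trial, whose secondary objective reads "To determine which laser system (if any) offers superior efficiency". The endpoint table beside that objective names only fragmentation speed, lasing activity and energy utilization. The status of operative time as an endpoint therefore rests on the synopsis and Section 9.3.3, which are enough.

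Third, the magnitudes depend on assumed inputs. This stands. The largest figures need a 1 SD shift and correlations of 0.5; at 0.25 to 0.5 SD the type I error is only 5.6% to 6.5%. Part of the power loss at 1 SD is collinearity and not bias.

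Finally, operative time might be meant as a proxy for case complexity. Stone volume and number of stones serve that purpose, can be fixed before surgery and are already named in Section 9.3.1.

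**Conclusion.** The concern holds. Operative time is misclassified as a confounder in Section 9.3.2: it arises after allocation, it is a secondary endpoint, and no stated estimand justifies conditioning on it. That conclusion follows from the documents and needs no assumption.

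The consequence is conditional. If the laser does not change operative time, the adjusted effect is not biased. If it does, adjustment can hide a real effect, create a spurious one or shrink a true one, and the direction depends on which laser is faster. Under the assumed inputs, the damage at the planned size runs from negligible at no shift to a type I error near 10% and power near 42% at a 1 SD shift. The size and direction in this trial are unknown.

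The unadjusted comparison is sound on this point. The plan should be corrected before analysis, but the defect does not undermine the design.

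**What to change.** Remove operative time, and every other intraoperative measure, from the model that estimates the laser effect on stone-free status. Replace the open-ended reference to further confounders with a closed list. Suggested text for Section 9.3.2:

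> The adjusted analysis is a logistic regression of stone-free status on laser arm, with stone volume and number of stones from the preoperative CT as covariates. Only variables measured before surgery, and so not affected by the laser assigned, enter this model. The laser effect is reported with its 95% confidence interval.

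Three further points:

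- State whether the unadjusted or the baseline-adjusted comparison is primary. The unadjusted one matches the basis of the sample size in Section 9.1, but either removes the defect.
- State that this is the same model as the regression in Section 9.3.1. Include patient position only if it is fixed before allocation.
- Keep operative time as a secondary outcome. If a model with operative time is still wanted, label it exploratory and do not present its laser coefficient as the treatment effect.

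The cost is wording only. Section 5.1 already requires a preoperative CT, Section 9.3.1 already names the covariates, and the sample size does not change.

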# **5 STUDY POPULATION**

#### 5.1 INCLUSION CRITERIA

- Undergoing single stage unilateral RIRS for total stone burden volume >5mm to < 20 mm
- Must have preop CT scan to measure HU and measurements

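### The adjusted stone-free analysis in section 9.3.2 controls for operative time, which is measured after laser assignment and is itself an endpoint; it should come out of that model

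*Combined protocol and SAP*

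**What the plan says.** Section 9.3.2 describes two analyses of stone-free status. The first is unadjusted: "Stone free rates for each laser will be analyzed using the Kruskal-Wallis statistical test". The second is a regression whose purpose is to "control for stone size, operative time, and other potential confounders". The type of regression is not stated, nor is which result stands if the two disagree.

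On timing, section 6.1.1 says "randomization will occur preoperatively". Section 6.3 has the study IDs randomised before the study starts, and the schedule in 1.3 places randomisation on the day of surgery. On each account, assignment comes before any operative time exists.

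On the role of operative time, the synopsis lists it, in minutes, among the secondary endpoints. Section 9.3.3 includes it in the comparison by laser: "lasing activity, operative time, lasing time, lithotripsy time, and treatment time will be analyzed using Kruskal-Wallis statistical tests". The section 3 table is shorter and omits it, naming only fragmentation speed, lasing activity and energy utilization.

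Section 9.3.1 plans a separate logistic model with "candidate predictors chosen a priori, including patient position, number of stones, and stone volume". Operative time is not named there.

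**The concern.** The plan gives one variable two incompatible roles. In 9.3.3 operative time is a possible result of the laser; in 9.3.2 it is a confounder of the laser's effect. A confounder has to influence which treatment is received. Under randomisation nothing measured during surgery can do that.

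Adjusting for it can go wrong in two ways:

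- **Mediation.** If a laser clears stones better partly because it works faster, holding time fixed removes that part of its benefit.
- **Shared causes.** If unmeasured difficulty drives both time and clearance, and the lasers differ in speed, patients with equal operative times in the two arms are not alike. The model then compares unlike patients, even where the lasers have the same stone-free rate.

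The research question in the synopsis is which laser has the better stone-free rate. No section says that an effect at fixed operative time is wanted. At stake is whether the adjusted result, reported under the primary endpoint, answers the trial's own question.

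**Working it through.** **1. The plan's own figure.** Section 9.1 uses 66% vs 33%, 80% power, 5% alpha and 1:1 allocation. With the unpooled two-sided formula:

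n = (1.960 + 0.842)² × (0.66×0.34 + 0.33×0.67) / 0.33² = 7.849 × 0.4455 / 0.1089 = 32.1, so 33 per arm and 66 in total.

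Allowing for 20% dropout, 66/0.8 = 82.5, against 82 stated. The sample size is reproduced. It rests on two unadjusted proportions, so removing a covariate does not change it.

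**2. What has to be assumed.** The documents do not give:

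- d = thulium minus holmium mean operative time, in within-arm SDs;
- r = correlation of operative time with the tendency to be stone-free, given arm and stone size.

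**3. Model.** A = 1 for thulium, 0 for holmium; S (stone size), e and f are independent standard normal.

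- Stone-free if -0.4S + √0.84·e + Φ⁻¹(p_arm) > 0. The arm rates are then exactly p_arm whatever d is.
- Operative time T = dA + 0.5S + √0.75·(r·e + √(1-r²)·f), with within-arm SD 1.
- Logistic regression, two-sided 5% Wald test of A, with and without T; 20,000 simulated trials per case.

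**4. Results with 33 per arm and thulium 0.5 SD faster (d = -0.5).**

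| r | Power at 66% vs 33%: without T → with T | False positives at 50% vs 50%: without T → with T | Excess favours |
|---|---|---|---|
| -0.3 | 81% → 64% | 5% → 8% | holmium |
| -0.1 | 81% → 72–73% | 5% → 5% | little excess |
| +0.3 | 81% → 91% | 5% → 8% | thulium |

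At r = -0.5 power with T is about 55% and false positives about 14%, favouring holmium. With thulium slower (d = +0.5) and r = -0.3, false positives are again about 8%, now favouring thulium.

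**5. Not all of the power change is bias.** T is correlated with A when d ≠ 0, so including it widens the standard error even at r = 0. At d = -0.5, given S, the R² of A on T is (0.5×0.25)² / (0.25 × (0.75 + 0.25×0.25)) = 0.0156/0.203 = 0.077. The standard error therefore grows by 1/√(1-0.077) = 1.04. Power of 81% corresponds to 1.96 + 0.88 = 2.84 standard errors; 2.84/1.04 = 2.73, which gives power of about 78%. The rest of each change is bias.

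**6. Equal times (d = 0).** There is no bias. At r = -0.3 power is about 83% with T and 81% without, a small precision gain.

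**7. A differently built check** (logistic models, 400,000 patients per case, parameters again assumed):

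- Laser acting wholly through time: odds ratio 1.87 unadjusted, 0.99 adjusted for time.
- No laser effect on clearance, one laser faster, hidden difficulty driving time and clearance: about 1.0 unadjusted, 0.79 to 0.65 adjusted.
- No laser effect on time or clearance, same hidden difficulty: 0.99 with or without adjustment.

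**The case against.** The strongest reply is that only an additional analysis is affected. Section 9.3.2 puts the unadjusted comparison first, and the sample size is built on it, so a valid randomised result will exist whatever the regression shows. This stands, and it limits the weight of the point. A reader might infer that the trial's primary comparison is biased; the documents do not support that. That the plan does not rank the two results is a separate gap.

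A second reply concerns direction. It is tempting to conclude that adjustment would understate thulium, on the view that thulium is faster and long cases clear less well. No section supports either premise. Longer operating could equally mean more thorough clearance, and a positive r reverses the bias. With a weak correlation false positives barely move. This objection also stands.

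Third, the figures use 33 per arm. With no dropout and 41 per arm, power at d = -0.5, r = -0.3 falls from 89% to 73%, so the level is higher but the fall is similar.

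Fourth, the section 3 table does not list operative time as an endpoint. That inconsistency is real but not decisive, because measurement after assignment is enough on its own.

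A reader might also extend the point to patient position, which 9.3.1 names as a predictor. Nothing in the documents suggests that position depends on the laser, so the point does not reach it.

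**Conclusion.** The point holds for the adjusted analysis in 9.3.2 and no further. Operative time follows assignment and is an endpoint of the same comparison, so calling it a confounder is wrong as written. Bias arises only if the lasers differ in operative time and time is related to stone-free status beyond stone size. The documents give neither value, so both its direction and its size are unknown. The simulated figures show that it could matter at this sample size; they do not predict this trial. They assume a logistic model, because 9.3.2 names no model type, and values of d and r that have no source in the documents. The change should be made before the data are analysed.

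**What to change.** In section 9.3.2:

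- Delete operative time from the laser-effect regression. Keep it as a secondary endpoint under 9.3.3.
- Name the adjusted model: laser, stone volume and number of stones. The last two are already chosen in 9.3.1.
- If operative time was meant to stand for stone difficulty, use Hounsfield units from the scan that section 5.1 already requires: "Must have preop CT scan to measure HU and measurements".
- Replace the open-ended last item in the covariate list with *variables measured from preoperative data*. Wording that required recording before assignment would fit badly with section 6.3, where IDs are randomised before any patient is seen.

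The cost is a wording change: no new data, visits or patients, and no change to the unadjusted test or the sample size. The one loss is the small precision gain if the lasers take equal time, about 83% versus 81% power at r = -0.3.
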